**Serological Testing:** Serology will establish background immunity levels in students and staff, from infection or vaccination, and will follow those who are antibody-positive longitudinally to quantify temporal decay of IgG and neutralizing antibody levels. We will determine whether protective immunity in children with IDD, a population with prevalent immunological dysfunction, wanes at an accelerated rate compared to the population-at-large; by doing so we will address an important knowledge gap, and provide key data to inform public health policy. **3) Modeling to Optimize Testing:** We will use network models and agent-based simulation models (or hybrid approaches) to guide testing strategies and interventions at MCC. Simulations will be conducted interactively and iteratively, to assist in planning and implementation of testing procedures, exploring the dynamic interplay between school operations and personnel interactions, potential infection risks and disease dynamics (including variant strains), and implementation of control measures (e.g. quarantine, isolation, contact-tracing and vaccination rates). **4) Mobile Unit Testing:** We build on our successful mobile approach to delivering mobile dental care to the IDD students of MCC (the SMILEmobile), by staffing, equipping and deploying a customized, disability-enabled, mobile testing unit equipped with a specialized HEPA-filter enabled HVAC system (**UR Health in Testing - HIT Mobile**). We will use this to directly deliver rapid flexible testing to MCC. **5) Overcoming Testing & Vaccine**

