### Scientific Goal 2: Serological Testing and Modeling

The dynamics of the immune response to SARS-CoV-2 are as yet unknown in children with IDD, a population with prevalent immunological dysfunction, who may show different COVID-related immunological profiles and latencies to those of the general population. Here, we longitudinally follow those with IDD identified as antibody-positive, from either infection or vaccination, to quantify the timing of reductions in IgG and neutralizing antibody levels. We will use a combination of the SARS-CoV-2 clinical serological assay (described above), and a research multiplex assay for anti-spike and nucleocapsid protein IgG and receptor binding domain (RBS) antibodies, against SARS CoV-2 (including emerging virus variants), and a panel of commonly circulating human coronaviruses. *This will provide serological data uniquely focused on the IDD population with clear implications for public health immunity strategies.*

**Experimental Approach.** IgG responses to individual SARS-CoV-2 antigens (S, NP, RBD) in enrolled students and staff will be measured initially by clinical testing and fingerstick at baseline, and then every four weeks by fingerstick for up to 36 months. Any large increase in anti-SARS-CoV-2 levels will be confirmed by clinical serology. Dynamics of anti-SARS-CoV-2 IgG will be assessed by fitting the anti-S, NP and RBD quantitative results to a modified power law model that accounts for long-term antibody persistence:  $f(t) = k + \log [(1 - \lambda)(c + t)^{-\alpha} + \lambda]$ , where  $k$  is the peak log IgG level,  $\alpha$  is the decay rate,  $c$  is a constant, and  $\lambda$  is the steady-state long-term IgG level. We will fit the model using a mixed effects

**Figure 1 – Serological Testing.** (A) Clinical analysis of persistence of anti-S, anti-NP, and anti-RBD binding IgG and PCR results from the URMC Clinical Laboratory. Note the early decline of anti-NP IgG. (B) Multiplex testing for IgG directed against S proteins for common circulating coronaviruses, including SARS-CoV-2 (SARS2), and prior SARS-CoV-1 and MERS (Middle East Respiratory Virus)

method, where  $k$  and  $\alpha$  are subject specific random effects drawn from a bivariate normal distribution. This will allow comparison of decay rates ( $\alpha$ ) and steady state anti-SARS-CoV-2 IgG levels ( $\lambda$ ) across subjects.

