## 2. CHARACTERISTICS OF THE RESEARCH POPULATION

### 2.1 Subject Characteristics

All staff and students at Mary Cariola Center (MCC) are eligible for this study

**a) Number of Subjects** – There are 500 on-site staff and 450 students. Up to 950 people may enroll, although we expect around 70% enrollment

**b) Gender and age of subjects** – Among MCC **employees**, approximately 75% are female. We expect at least 50% to consent to testing and another 30% to complete the baseline survey.

**Among students under age 18**, approximately 30% are female, consistent with the national IDD population. We expect 70% to enroll. Unless our enrollment trends show otherwise we do not anticipate any unique messaging or additional outreach to achieve our enrollment target. There are also Mary Cariola students age 18-21 approximately 30% female.

**There are no exclusions by age** however we are limited by the ages of those attending or residing in MCC and the age range of employees.

**MCC students** are included in this study as the main participants as the study seeks to understand testing and transmission patterns among individuals with IDD in school and residential settings including modeling. Most of the students in the school setting are under age 18; The youngest student is age 3. There are also about 60 students at the school between the ages of 18-21. Approximately one third of these students have legally authorized representatives (guardians).

Age distribution of students is:

3-5	20%
6-10	28%
11-14	25%
15-17	19%
18-21	8%

We will track early enrollment to determine if rates are lower than expected or if there are under-represented age groups (based on the age distribution of MCC students). This will warrant revising of recruitment strategies and tactics within the research team and the CAB.

**MCC Staff** range in age from 18 to 75.

STUDY #: 5294

Version Date: 04/17/2023

Page 9 of 27

Efforts to enroll employees will be informed by the CAB. We will track early enrollment to determine if rates are lower than expected or if there are under-represented age groups. Lower than anticipated enrollment will warrant revising of recruitment strategies and tactics within the research team and informed by the CAB.

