## **Genetic Research Procedures**

*Banking of DNA samples for mRNA vaccine response and IgG level decay targeted genotyping:*

**Blood Sample** - One tube (one tube – 6-10ml) of blood will be collected from up to 200 neurotypical staff and 50 IDD students and stored for later DNA isolation and targeted genomic analysis. This is genomic research and NOT genetic testing. It will be carried out for research purposes only and no information about genetics will be disseminated to participants. After all testing is completed samples will be destroyed.

Population (Minor vs. Adults)	Blood Draw Procedure (COVID antibodies, MBC, or DNA)	Amount of Blood	Frequency of Blood Draw	Fingerstick or Venipuncture
Adults	COVID anti	1-2 drops	monthly	fingerstick
Minors	COVID anti	1-2 drops	monthly	fingerstick
Adults	COVID	6-10 cc	Every 6 months (completed)	Veni.
Minors	COVID	6-10cc (unless under age 5 (then 3- 5cc)	Every 6 months (completed)	Veni.
Adults	MBC	6-10 cc	Once only	Veni.
Minors	MBC	6-10cc (unless under age 5 (then 3- 5cc)	Once only	Veni.
Adults	DNA	6-10cc	Once only	Veni.
Minors	DNA	6-10cc (unless under age 5 (then 3- 5cc)	Once only	Veni.

**Mandated COVID-19 testing for Mary Cariola Staff:** In response to the New York State vaccine mandate Mary Cariola Center policy requires **staff who are not vaccinated** to be tested weekly for COVID-19. One method for meeting this policy requirement is enrollment in this study. Staff who are enrolled will be tested weekly and results reported to Mary Cariola personnel. **For all unvaccinated staff enrolled in the study** missing the scheduled weekly COVID test will be reported to Mary Cariola administrative personnel in accordance with Mary Cariola Center policy.

**Other data.** MCC will also provide student and staff schedules (i.e. what room they are in) for use in the modeling

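### The waning claim against the general population has no designated comparator, and a student–staff contrast could not separate IDD from age

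*Protocol*

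**What the plan says.** Protocol section 1.3, under serological testing, sets a comparative aim: "We will determine whether protective immunity in children with IDD, a population with prevalent immunological dysfunction", "wanes at an accelerated rate compared to the population-at-large". It presents the answer as input to public health policy.

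The people sampled are those of one school. The same section says "Serology will establish background immunity levels in students and staff, from infection or vaccination", and section 2.1 says "All staff and students at Mary Cariola Center (MCC) are eligible for this study". The criteria in section 2.2 admit IDD students aged 3–21 and staff aged 18–72; section 2.1 describes staff who "range in age from 18 to 75".

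Scientific Goal 2 fits a modified power-law decay curve with subject-level random effects for the peak level k and the decay rate α. It adds: "This will allow comparison of decay rates" and steady-state levels across subjects. It states no term for student or staff status, age or immunising event, and it does not say from which event time is counted.

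The SAP repeats the premise that protection may last less long in IDD, but plans only descriptive statistics for immunity levels. It names no comparator and no adjustment.

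**The concern.** A statement about IDD children relative to the general population needs non-IDD people who resemble those children in age and exposure. The plan has none. Staff are the only non-IDD participants the criteria admit, and they are all adults.

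Children and adults may lose antibody at different rates for reasons unrelated to IDD. The two groups may also differ in their mix of infection and vaccination: the Contingency Plans paragraph expects vaccine approval for under-16s to arrive during the study. Either difference would pass straight into a student–staff comparison of α. The risk is that an ordinary child–adult difference, or a difference in exposure, is reported as an immune deficit in IDD and carried into policy.

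**Working it through.** Neither document gives a sample size, power, error rate or effect size for this comparison, so there is no planned figure to reproduce.

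**1. Age overlap (section 2.1)**
- The student age table puts 8% at ages 18–21: 0.08 × 450 = 36. The text says about 60: 60/450 = 13.3%.
- Students under 18 are therefore 92% or 86.7% of the total. No eligible non-IDD participant is under 18.

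**2. Numbers with quantitative antibody data**
- Section 2.1 states: "There are 500 on-site staff and 450 students. Up to 950 people may enroll, although we expect around 70% enrollment". At 70% that is 350 staff and 315 students.
- Goal 1 limits the research assay to 200 subjects; Goal 2 reads as if all enrolled students and staff were measured. Splitting the 200 pro rata (assumed) gives 200 × 450/950 ≈ 95 students and 105 staff.
- Students aged 18–21: 94.7 × 0.08 = 7.6 to 94.7 × 0.133 = 12.6, so about 8–13. If all enrolled students have quantitative data: 315 × 0.08 = 25 to 60 × 0.7 = 42.

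**3. Chance of reading an age effect as IDD**

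Assume no IDD effect, a 0.3 SD child–adult step in decay rate, and a two-sided 5% test. The expected student–staff difference is 0.3 × 0.92 = 0.276 SD or 0.3 × 0.867 = 0.26 SD. With z = difference / √(1/n₁ + 1/n₂), the rejection probability is approximately Φ(z − 1.96).
- 95 v 105: z = 0.276/0.1416 = 1.95 gives 50%; z = 0.26/0.1416 = 1.84 gives 45%.
- 315 v 350: z = 0.276/0.0777 = 3.55 gives about 94–95%; z = 3.35 gives 92%.
- 315 v 250 (section 2.1 elsewhere expects at least 50% of employees to consent to testing): z = 3.26 and 3.07 give about 90% and 87%.

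At 95 v 105, assumed steps of 0.2 and 0.5 SD give 23–25% and 86–90%.

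**4. Does a linear age term repair it?**

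The staff age distribution is not given. For the base case, take ages uniform over 18–72 completed years (mean 45.5, variance 55²/12 = 252.1). The student bands, uniform within band, give mean 11.3 and variance 24.7. Group weights are 0.474 and 0.526.
- Pooled within-group variance of age: 0.474 × 24.7 + 0.526 × 252.1 = 144.4. Between-group variance: 0.474 × 0.526 × 34.2² ≈ 292. So r² = 292/(292 + 144.4) = 0.67 and |r| = 0.82.
- Variance inflation is 1/(1 − 0.67) ≈ 3.0 and the standard error rises by √3.0 ≈ 1.7. This describes precision, not bias.
- For the bias, suppose only a step at 18. The share of the spurious difference left in the group coefficient is 1 − (within-group slope of the step on age × age difference)/(unadjusted difference).
- Within-student covariance: 0.92 × 0.08 × (10.5 − 20) = −0.70. Slope: 0.474 × (−0.70)/144.4 = −0.0023.
- Share left: 1 − (0.0023 × 34.2)/0.92 = 0.91.

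Simulation over four assumed staff age distributions (uniform to 72, uniform to 75, younger-skewed, mid-peaked) and both overlap figures gave:

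| Assumed age effect | Share left after linear adjustment |
|---|---|
| Step at 18 | about 74–92% |
| Linear to 25, then flat | about 55–70% |

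**5. Power in the overlap for a 0.5 SD difference, equal groups (assumed)**
- 8 v 8: z = 0.5/√(2/8) = 1.00, power 17%. 13 v 13: z = 1.27, power 25%.
- 25 v 25: 42%. 42 v 42: 63%.

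**The case against.** The strongest reply is that staff are never named as the comparator for waning. That is correct. Goal 2 speaks of following antibody-positive people with IDD. The phrase "up to 200 neurotypical staff and 50 IDD students" concerns DNA banking; it shows how the protocol regards staff but does not define decay-comparison groups. An external reference is not excluded: Figure 1 shows laboratory persistence data, the multiplex assay is used in other studies, and Goal 4 would offer enrolment to people found positive in nearby hotspot testing. None of these is designated as a reference group, the criteria contain no hotspot cohort, and no analysis uses one. What stands is that the comparator is unspecified and the only one available under the criteria is unsuitable.

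A second reply is that the protocol says only that it will determine whether waning is faster, and that the SAP is descriptive. Both are true. A reader might infer that the plan is bound to conclude in favour of faster waning; the documents do not say so. But a descriptive analysis does not deliver the determination promised, so the two still need reconciling.

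A third reply is that exposure source is partly covered. Goal 1 distinguishes infection from vaccination by antibody pattern, vaccination is to be recorded, and Goal 2 does not exclude covariates. So the data should exist and only the model terms are unstated.

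**Conclusion.** The concern holds in this form: the stated conclusion about the general population cannot be reached from the plan as written, because no comparator is designated and, for 87–92% of students, no non-IDD participant of the same age is eligible. This follows from the eligibility criteria and needs no assumption beyond taking staff as non-IDD.

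A reader might infer from the variance inflation of about 3.0 that adding age gives a valid estimate with a standard error about 1.7 times as large. That would be so only if decay rate changed linearly with age from 3 to the seventies. Below 18 the adjustment is extrapolation, and the main problem is residual bias of about 55–92% of the child–adult difference in the cases tried. Nor do 25–42 overlapping students provide a secure check: that range requires quantitative data on every enrolled student, and under the 200-subject limit it is about 8–13.

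The rejection rates depend on the assumed 0.3 SD effect and group sizes, and the residual shares on assumed staff ages and two assumed age-effect shapes. They illustrate the size of the risk and do not forecast a result.

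**What to change.** 1. In protocol section 1.3 and the SAP, replace the general-population claim with a description of antibody decay in IDD students. Any contrast with adult staff of the same school should be called exploratory and stated to be confounded with age and not attributable to IDD.
2. In the Goal 2 decay model, add group (student or staff) and immunising event (infection, vaccination or both), and count time from the last event. PCR, serology and vaccination records already supply these.
3. Show an age-adjusted estimate only as a sensitivity analysis. State that it extrapolates below 18 and that a linear term can leave most of a child–adult difference in the IDD coefficient.
4. Treat any contrast at ages 18–21 as descriptive. Reconcile the 8% and about-60 figures, the staff age limits of 72 and 75, and the 200-subject and all-enrolled accounts of the research assay.

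The cost is text and model terms, with no new participants or procedures. The price is a narrower claim and no formal conclusion about IDD against the general population.

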**Table 1: URMC COVID-19 Testing Capacity and Modalities**

Platform	Test	Capacity: Tests/Day	Certification
Roche 8800	Molecular	2000	FDA-EUA
Cepheid	Molecular	500	FDA-EUA
Hologic	Molecular	500-1000	FDA-EUA
Abbot Architect	Serology	1000	FDA-EUA
TF Amplitude	Molecular	3000-6000	FDA_EUA-pending

#### **1.4 CENTRAL AIMS**

**Scientific Goal 1: Establish a molecular testing program to monitor and identify COVID-19 infections within a school community of individuals with IDD**

**Overview and rationale:** This program will focus on the students (n=450) and staff (n=500) of the MCC, who collectively form a community that is highly representative of other IDD school communities across the nation. We will establish testing across this difficult-to-test population, using a tailored and flexible approach to foster test uptake and to prevent and/or mitigate COVID-19 outbreaks.

**Establish a clinical molecular and serological COVID-19 testing program for the Mary Cariola Center:** The dynamics of viral spread are unknown in a school serving individuals with IDD such as the MCC. Questions to be answered with *molecular* testing include: What is the incidence of asymptomatic COVID-19 infection, and how is this affected by rising vaccination rates? How do activities within the school alter risk? *Serological* testing will assess baseline prevalence of prior infection (anti-NP IgG), and changes over time, in response to infection (anti-NP IgG+) and vaccination (anti-S IgG+, anti-NP IgG-).

**Molecular Testing:** RT-PCR tests for SARS-CoV-2 with FDA EUA will deliver highly sensitive and specific clinical-grade results. Respiratory samples will be obtained by mid-turbinate or nasal swabs, collected in a dedicated area with proper ventilation and PPE (see Mobile Unit testing plan below), and delivered to the URMC Central Laboratory for testing in a CLIA environment with 24-72h turnaround times. The testing plan includes two groups: those tested as part of scheduled surveillance and those tested for symptoms or exposure.

**Surveillance Screening and Exposure/Symptomatic Testing:** Participants will be tested every 5-14 days to increase likelihood of detecting infected but asymptomatic individuals. Enrolled students and staff who report symptoms in the on-site screening will be tested on-site. Symptomatic individuals will be tested separately from asymptomatic participants every 3 days for up to 10 days. *Reported* test results will be qualitative, although Ct (cycle threshold) values will also be captured for modeling purposes.

**Clinical Serological Testing:** Tests with FDA-EUA will be used to assess the presence of IgG antibodies to SARS-CoV-2 (Table 1) every 6 months. Our current Abbott Architect assay qualitatively assesses IgG binding to the SARS-CoV-2 nucleocapsid (NP) protein and we intend to offer the Architect anti-spike (S) semi-quantitative assay when it is granted EUA (expected shortly). Serum will be collected upon enrollment and then every 6 months for the duration of the study period. Assuming 70% study enrollment, this will result in 1,680 staff and 1,330 student serological tests.

[figure not shown]
**Reporting and Result Handling:** The ordering provider ([name]) at the MCC and nursing staff will receive test results. Positive results will be reported to public health agencies via standard clinical protocols. Both molecular and serological *clinical* results will be qualitative (Positive, Negative, Inconclusive). Upon the communication of a positive molecular test result, students and staff will be referred to their primary care providers (PCPs) or urgent care if lacking a PCP. Enrolled study subjects who have been in close proximity to the positive individual will be immediately PCR tested. Unenrolled, exposed individuals will be offered study enrollment or else referred to their PCP/urgent care for testing. RT-PCR positive students will be re-tested every two weeks to assess viral load kinetics.

**Research Serological Testing:** Modeling requires continuous, quantitative data to estimate antibody persistence, and as a correlate of immunity. We will test 200 subjects every 4 weeks for up to 36 months using a multiplex research assay that simultaneously measures IgG levels against the spike (S) and nucleocapsid (N) proteins of SARS-CoV-2 and human seasonal strains (OC43, HKU1, NL63, 229E); we will also measure antibodies directed against the receptor binding domain (RBD) of the S protein. This assay provides absolute measures of serum IgG (ng/ml), and is currently in use in several NIH funded studies (see Fig 1). We are also adding emerging SARS-CoV-2 variants (e.g. UK, South African). Samples will be collected by fingerstick and volumetric micro-sampling (VAMS) to collect 40 $\mu$ l of capillary blood. A topical anesthetic cream can be used prior to collection. Samples will be analyzed by batch in [name] lab.

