## 4. METHODS AND STUDY PROCEDURES

### 4.1 Study Procedures and Assessments

*Funding of study elements:* A grant to the University of Rochester from the National Institutes of Health RADx-UP program is providing funding for all aspects of the study procedures with the exception of the fingerstick blood draw and analysis of these blood samples. The fingerstick test for COVID-19 antigens is not an FDA approved test – it is solely for research purposes. Funding for this aspect of the project comes from a separate grant from the National Institutes of Health as a supplement to the University of Rochester Intellectual and Developmental Disabilities research Center.

**Questionnaire:** Staff or parents of students will be sent a unique link to a RedCap form for them to fill out. We will arrange to send this to them via email or provide them with an opportunity to fill this out on-site using a study iPad. The questionnaires are designed to collect information about the household of the subject, demographics information, attitudes and opinions regarding COVID-19 risk and testing, and vaccines. Also asked are questions about medical history, health status, drug/alcohol use.

A second link to the questionnaire will be sent all current participants to collect a cross-section of responses at a single time point – beginning mid May 2022. The questionnaires will be identical to the initial questions presented to each participant at the time of their enrollment.

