#### **Asymptomatic Testing –**

**Nasal Swab:** Participating individuals (students and employees) will be tested for COVID-19 (RT-PCR) using a specimen collected using a mid-turbinete swab. This asymptomatic testing

STUDY #: 5294

Version Date: 04/17/2023

Page 13 of 27

regime starts on or after (if scheduling testing requires this to begin on a different day) enrollment and is repeated every 5-14 days for up to 36 months. Anyone testing positive is followed up as described below for symptomatic individuals.

**Saliva Sample:** For those participants (students only) that are unable to tolerate the nasal swab (mid-turbinate) test, we will use the Spectrum Solutions™ SDNA-1000 Molecular Diagnostic Saliva Collection Device. This is a self-contained, **EUA authorized** saliva collection system. It requires filling a small tube with saliva.

**Blood Samples:** Participating asymptomatic individuals (students and employees) will be tested for antibodies using the fingerstick upon scheduling first sampling visit and monthly thereafter for up to 36 months. This first blood sampling will be using a fingerstick and 1-2 drops of blood will be collected in a curette for serology testing. Possible complications include pain from the fingerstick, and a low risk of infection. The rationale for this intervention is to measure serum antibodies against SARS-CoV-2 using standard FDA approved testing methods.

A second method for blood sampling using venipuncture will be carried upon enrollment or upon scheduling the first sampling visit and subsequently, every six months for up to 36 months. In addition this method will be used for additional blood collection for MBC and DNA analyses. This second method will use venipuncture to collect ~6-10 cc of whole blood (except in students younger than 5 years in whom we will collect between 3-5cc). The possible complications of phlebotomy/venipuncture include pain, small local hematoma formation, bleeding and infection. However, this method of blood collection and testing is widely used by millions individuals daily in the United States with minimal complications, including IDD subjects. Phlebotomy will be conducted by a team specially trained in working with IDD subjects to minimize risk.

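### The protocol gives conflicting accounts of who has the monthly fingerstick IgG that feeds the decay model (200 subjects, or enrolled students and staff without a cap) and of the assay's approval status, and no comparator is specified for the IDD waning question

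*Protocol*

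**What the plan says.** **Size.** Protocol 1.4, Research Serological Testing, introduces the multiplex assay that gives absolute IgG concentrations from a fingerstick: "We will test 200 subjects every 4 weeks for up to 36 months". It does not say how the 200 are chosen or how many are students.

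**Who is followed.** Protocol 1.4, Scientific Goal 2, opens with a narrower group: "we longitudinally follow those with IDD identified as antibody-positive, from either infection or vaccination". Its Experimental Approach then says that IgG responses "in enrolled students and staff will be measured initially by clinical testing and fingerstick at baseline, and then every four weeks by fingerstick", and these quantitative results are fitted to the decay model. Protocol 1.3 says that serology, having set background immunity in students and staff, "will follow those who are antibody-positive longitudinally to quantify temporal decay of IgG and neutralizing antibody levels".

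**Procedures.** Protocol 4.1, Blood Samples, says that participating asymptomatic students and employees "will be tested for antibodies using the fingerstick upon scheduling first sampling visit and monthly thereafter for up to 36 months". No cap appears.

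**Assay status.** Protocol 4.1, under funding, says: "The fingerstick test for COVID-19 antigens is not an FDA approved test", and describes it as research-only. Blood Samples, later in 4.1, says of the fingerstick: "The rationale for this intervention is to measure serum antibodies against SARS-CoV-2 using standard FDA approved testing methods". The Phlebotomy paragraph of 6.1 repeats that statement.

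**The comparison.** Protocol 1.3 undertakes to determine whether protective immunity in children with IDD "wanes at an accelerated rate compared to the population-at-large". The Goal 2 model gives each subject a random peak level k and decay rate alpha from one bivariate normal distribution, and offers comparison only across subjects. The SAP says immunity may last less long in IDD populations, but plans descriptive statistics for immunity levels. It contains no decay model, decay population, comparator or group test.

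**The concern.** The 200-subject statement and the uncapped statements share the same interval, duration, sampling method and SARS-CoV-2 antigens, so they appear to describe one activity with two different sizes. Someone fitting the decay model could follow either and be within the protocol.

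The choice affects the one comparative immunological claim that the study makes. Staff are the only non-IDD group sampled. If the analysis follows the opening of Goal 2 literally, staff drop out and no within-study contrast remains. If 200 are assayed, the precision of a student-staff contrast depends on a split that nobody has set. If everyone is assayed, precision is much better. A finding of no faster waning would carry different weight in each case, and the report could not be checked against the plan.

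The conflict over assay status is a second inconsistency. It does not define the cohort, but it also appears in the risk section. It also weakens the natural way out of the size conflict, which is to suppose that the uncapped fingersticks are for a different, clinical test.

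**Working it through.** **1. The stated figure.** The 200 cannot be reproduced. Neither document gives a significance level, power, effect size, SD, split or dropout rate for it. It can only be compared with expected enrolment.

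**2. Expected enrolment (Protocol 2.1).** There are 450 students and 500 staff. About 70% are expected to enrol, and at least 50% of staff to consent to testing.

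- Students: 0.70 × 450 = 315
- Staff: 0.50 × 500 = 250 to 0.70 × 500 = 350
- Total: 315 + 250 = 565 to 315 + 350 = 665
- Share assayed if 200: 200/665 = 30% to 200/565 = 35%
- Ratio: 565/200 = 2.8 to 665/200 = 3.3

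**3. The statements side by side.**

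| Place | Who | Number |
|---|---|---|
| 1.4 Research Serological Testing | unspecified subjects | 200 |
| 1.4 Goal 2, opening | antibody-positive people with IDD | none given |
| 1.4 Goal 2, Experimental Approach | enrolled students and staff | no cap (565 to 665 expected) |
| 1.3 Serological Testing | antibody-positive, from students and staff | none given |
| 4.1 Blood Samples | participating asymptomatic students and employees | no cap |
| SAP | no decay population | none given |

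Rows 1 and 3 conflict directly, and row 5 agrees with row 3. Rows 2 and 4 could be analysis subsets of a wider sampled cohort, but the text does not say so.

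**4. Illustration of what the choice does to precision.** All inputs except the enrolment counts are assumed: two-sided 5%, 80% power, a two-sample normal comparison of subject-level alpha with equal SD, no attrition, and every subject contributing a curve. The splits are assumed too. Results are in SDs of alpha.

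Detectable difference = (1.960 + 0.842) × √(1/n₁ + 1/n₂)

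| Students / staff | Detectable difference (SD) |
|---|---|
| 315 / 350 (all enrollees) | 0.22 |
| 315 / 250 (all enrollees, staff at 50%) | 0.24 |
| 158 / 175 (half of each group antibody-positive) | 0.31 |
| 158 / 125 (same, staff at 50%) | 0.34 |
| 100 / 100 (200, even split) | 0.40 |
| 50 / 150 (200) | 0.46 |
| 25 / 175 (200) | 0.60 |

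At an assumed true difference of 0.3 SD, power is 94% to 97% with all enrollees, about 71% to 78% if half are antibody-positive, and 56% with 200 split evenly. With IDD participants only, no two-group figure exists.

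**5. Age.** Students are 3 to 21 and staff are 18 or over (Protocol 2.1). They overlap only at 18 to 21. That band holds 8% of students in the age table, or 60/450 = 13% by the count in the text above it.

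**The case against.** **The antibody-positive wording may be only an analysis subset.** A decay curve needs antibody to decay, so this is a fair reading. The documents therefore do not support the inference that there are three mutually exclusive cohorts. What stands is that the restriction is not stated as a subset rule and, read literally, excludes staff.

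**Perhaps fingersticks are collected from all and 200 are assayed.** That would remove the size conflict, but it is nowhere stated, and Goal 2 says that responses in enrolled students and staff are measured. On this reading 565 − 200 = 365 to 665 − 200 = 465 participants would give monthly research-only samples with no stated assay.

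**Support for the missing cap is narrower than it may look.** The payment terms in 4.4 and the blood-draw table in 4.1 price or list fingersticks without saying that everyone has them. Accepted: the point rests on the Goal 2 Experimental Approach and 4.1 Blood Samples.

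**A comparator is named.** It is the population-at-large. That is correct, but no data source or size is given.

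**The power contrast rests on assumed inputs.** Also correct. A reader might infer that the study is underpowered, but the documents plan no powered test, and the gap narrows if many enrollees are antibody-negative. Restricting enrollees to antibody-positive people raises the detectable difference. If the 200 are themselves chosen as antibody-positive, their figures do not change.

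**The genetic banking ceilings.** A reader might take the 200 staff and 50 students in 4.1 as the IgG cohort. The text does not support this. They are upper limits for a separate one-time collection, and nothing requires donors to have a monthly curve.

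**Conclusion.** The inconsistency is real and the SAP does not resolve it. The assayed cohort is either 200 or an uncapped group expected to be 2.8 to 3.3 times as large, with no selection rule or split if it is 200. The approval status of the fingerstick test is stated in opposite ways. The promised IDD waning comparison has no identified comparator data, no group term in the model and no place in the SAP.

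This is an internal inconsistency, not a miscalculation. The size conflict rests on the enrolment expected in Protocol 2.1. The detectable differences (0.22 to 0.24 SD against 0.40 SD or more) are illustrative and depend on the assumptions listed in the working.

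A reader might also infer that a larger or fixed staff group would settle the IDD question. It would not. Student status is largely confounded with age, so a student-staff difference in decay could not be attributed to IDD alone. The documents should be corrected before the decay model is fitted.

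**What to change.** **Protocol.** Reconcile 1.3, 1.4 and 4.1 to one statement of:

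- who gives monthly fingersticks;
- whose samples are run on the multiplex assay;
- if 200 stands, how they are selected and how many are students and staff.

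If more people are sampled than assayed, say what the other samples are for. Reconcile the funding paragraph and Blood Samples in 4.1, and Phlebotomy in 6.1, on the status of the fingerstick assay.

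**SAP.** Name the decay-analysis population, including any restriction to antibody-positive people, and name the comparator.

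- If staff are the comparator: add a student/staff fixed effect on alpha, adjust for age as far as the limited overlap allows, and report the effect with its confidence interval. State that IDD status is largely confounded with age.
- If only people with IDD are analysed: name the external comparator and its data source, or drop the comparative claim.

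**Cost.** Text edits to 1.3, 1.4, 4.1 and 6.1, and about one paragraph in the SAP. The edits themselves need no added participants or procedures. If sampling is already under way, the SAP should record who has actually been assayed. The documents do not establish that unassayed fingerstick samples remain from which to choose a different set.
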